3.1 Primary and secondary variables

The primary variables are all safety-related and include:

- Incidence of and severity of radium-223 dichloride/placebo related AEs
- Incidence of radium-223 dichloride /placebo related SAEs
- Incidence of leukemia, myelodysplastic syndrome, aplastic anemia, and primary bone cancer or any other new primary malignancy
- Incidence of bone fractures and bone-associated events (e.g., osteoporosis) regardless of investigator assessment of causality
- In participants who receive cytotoxic chemotherapy: incidence of febrile neutropenia or hemorrhage during their chemotherapy treatment and for up to 6 months thereafter at a frequency based on local clinical practice

Page: 6 of 17

Protocol No.: **BAY 88-8223/16996** Page: 7 of 17

4. Analysis Sets

4.1 Per-Protocol Analysis Sets

The following analysis set is defined per Protocol Amendment 2:

• Safety: All subjects who have received at least 1 dose of radium-223 dichloride or placebo in the feeder trials. This safety population will be used in the analysis of all safety endpoints. Subjects will be included in the analyses according to the treatment they received.

Per the Sponsor decision, a reduced and simplified analysis focusing on long-term safety data collected in study 16996 will be performed. Feeder trial data from patients not enrolled in 16996 will not be combined, therefore, the Safety analysis set defined per-protocol will not be implemented in the analyses described in this SAP. Instead, the Safety analysis set during long-term follow-up (SAF-LTF), as described in the table below (Section 4.2), will be used for safety analyses.

4.2 Per-SAP Analysis Sets

The following analysis sets will be used for the analyses described in this SAP:

Analysis Set	Description	
Enrolled analysis set (ENR)	All participants who signed an informed consent to study 16996 will be included in the Enrolled analysis set.	
	The Enrolled analysis set will be used for reports on 16996 study disposition and study conduct.	
Safety analysis set during long-term follow-up (SAF-LTF)	All participants who have received at least 1 dose of radium- 223 dichloride or placebo in an eligible feeder trial and who have signed informed consent to 16996.	
	The Safety During Long-term Follow-Up analysis set will be used for analyses of long-term safety in study 16996.	

Additional assignment details

For summaries based on the ENR analysis set by treatment group, participants who were assigned to treatment but not treated in the feeder trial will be classified based on assigned treatment group.

Unless otherwise specified, participants who enrolled in study 16996 but did not previously participate in an eligible feeder trial will be included in the overall totals in summaries based on the ENR analysis set, but will not be included in groupings by feeder trial or treatment group.

Protocol No.: **BAY 88-8223/16996** Page: 8 of 17

5. General Statistical Considerations

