### **3.3 Justification of the design**

This is primarily a descriptive safety study. All subjects enrolled in this study will have received at least 1 dose of radium-223 dichloride or placebo in the selected feeder trials and will be included in the safety evaluation. The subject population will include subjects treated with placebo and will therefore allow the comparison of the long-term safety profile with and without treatment with radium-223 dichloride.

The procedures chosen for the evaluation of long-term safety in this study population are consistent with the ethical standards used in studies of oncology drugs, and are appropriate for the long-term safety evaluation of subjects from the feeder trials.

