Per protocol, febrile neutropenia and hemorrhage AEs are to be collected during and within 6 months of cytotoxic chemotherapy treatment. For the protocol-specified analysis of the incidence of febrile neutropenia or hemorrhage during their chemotherapy treatment and for up to 6 months thereafter, a simplified analysis will be performed, of febrile neutropenia and hemorrhage AEs without regard to cytotoxic chemotherapy association. All 16996-emergent febrile neutropenia and hemorrhage AEs documented in the study CRF will be reported, without regard to chemotherapy treatment.

For the analysis of fractures and bone associated events, separate analyses of patients with bone fractures, patients with bone associated events, and patients with bone fractures and/or bone associated events will be performed. The applicable MedDRA appendix will identify the MedDRA preferred terms applicable to each sub-category.

Unless otherwise specified, the analysis for each AE category will include a summary of the total number and percent of SAF-LTF participants with an AE of the applicable category. Participants with an applicable AE will be summarized by MedDRA preferred term (PT), overall within each applicable MedDRA system organ class (SOC), and overall (any applicable AE), both by worst CTCAE grade and for any grade. For summaries by worst grade, the AE with the worst grade in the applicable summary category will be used. AEs with missing grade will be included in any-grade summaries but not in summaries by worst grade. In addition, listings will be provided.

6.4.2.1 16996-Collected Adverse Events

All AEs collected in study 16996, whether or not collection was required per study 16996 protocol, will be listed for SAF-LTF including AE PT, 16996-emergent (Y/N), start and stop dates, grade, treatment-related (Y/N), serious (Y/N), reason for seriousness, outcome of AE, and time (days) since last dose of study drug. The listing will include all 16996-collected AEs, whether or not emerging within study 16996.

6.4.2.2 16996-Emergent Adverse Events

Summaries of the total number and percent of SAF-LTF participants with an AE of the following categories of 16996-emergent AEs will be presented:

• All 16996-emergent adverse events

Statistical Analysis Plan

Protocol No.: BAY 88-8223/16996

Page: 13 of 17

- Radium-223 dichloride- or placebo-related 16996-emergent AEs;
- Radium-223 dichloride- or placebo-related serious 16996-emergent AEs;

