6.4.2.3 Deaths

The number and percent of participants with deaths, and the primary cause of death (as reported by the investigator), will be tabulated and listed for SAF-LTFU participants.

Protocol No.: **BAY 88-8223/16996** Page: 14 of 17

7. Document History and Changes in the Planned Statistical Analysis

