7.2 Changes in Per-Protocol Planned Statistical Analyses

Per the Sponsor decision to perform a reduced and simplified analysis focusing on data from study 16996, the following deviations from the per-protocol planned analyses have been noted in this SAP:

- Section 4. Analysis Sets
 - o Addition of of ENR and SAF-LTF analysis sets
 - o Removal of SAF analysis set;
 - Accounting for the assignment of participants enrolled in 16996 from non-eligible feeder trials.
- Section 5. General Statistical Considerations
 - o Removal of safety data combination between feeder studies and study 16996;
 - Description of limited data integration (including baseline characteristics and exposure);
 - o Description of interim safety analyses to meet Health Authority requirements.
- Section 6. Statistical Methodology
 - Summary of all febrile neutropenia and hemorrhage events collected in study 16996 without regard to chemotherapy treatment;
 - o Definition of 16996-emergent AEs.

Protocol No.: **BAY 88-8223/16996** Page: 17 of 17

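### If any enrollee from a non-eligible feeder trial was exposed to radium-223, that person's malignancy or fracture would appear in no planned AE table or AE listing

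*SAP*

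**What the plan says.** SAP Section 4.1 sets aside the protocol's Safety set: "Instead, the Safety analysis set during long-term follow-up (SAF-LTF), as described in the table below (Section 4.2), will be used for safety analyses". SAP Section 4.2 defines SAF-LTF as participants with at least one dose of radium-223 "dichloride or placebo in an eligible feeder trial and who have signed informed consent to 16996". The same section defines the enrolled set (ENR) as everyone who signed the 16996 consent, and limits its use: "The Enrolled analysis set will be used for reports on 16996 study disposition and study conduct".

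Section 4.2 then states what happens to people who enrolled without having been in an eligible feeder trial: they "will be included in the overall totals in summaries based on the ENR analysis set, but will not be included in groupings by feeder trial". Treatment groupings leave them out too. SAP Section 7.2 records this among the departures from the protocol as "Accounting for the assignment of participants enrolled in 16996 from non-eligible feeder trials", and the document history in Section 7.1 mentions it too.

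For the outputs, SAP Section 6.4.2.1 says that all AEs collected in 16996, "whether or not collection was required per study 16996 protocol, will be listed for SAF-LTF". Deaths, in SAP Section 6.4.2.3, "will be tabulated and listed for SAF-LTFU participants". The SAP does not define that last label. I read it as SAF-LTF.

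Protocol Section 3.3 states the premise of the design: "All subjects enrolled in this study will have received at least 1 dose of radium-223 dichloride or placebo in the selected feeder trials", and goes on to say that these subjects are all in the safety evaluation.

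**The concern.** The SAP makes room for a group of enrollees and then gives their adverse events nowhere to go. Under the protocol, sites report every new primary malignancy as an SAE, and every fracture as an AE or SAE, whatever the causality assessment. Any such event in this group would therefore be in the 16996 database. The one listing written to be exhaustive, covering even AEs whose collection was not required, is cut back to SAF-LTF.

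This matters because the study is descriptive and looks for rare, late events after exposure to an alpha emitter. An error over which trial a person came from does not undo an exposure. There can be good reason to keep such a person out of by-arm percentages. It is harder to justify leaving the event out of the listings as well.

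**Working it through.** No arithmetic applies. The claim concerns which analysis set each output uses, and the study has no sample-size or power calculation to reproduce. The check follows one hypothetical person through the SAP: enrolled in 16996, exposed to radium-223, and from a trial the SAP does not count as eligible.

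1. Membership. The person signed the 16996 consent, so is in ENR. The person has no dose in an eligible feeder trial, so is not in SAF-LTF (SAP Section 4.2).

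2. Feeder data. SAP Section 5.2.1 merges data from eligible feeder studies only, so this person's dose and arm are not brought in.

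3. Outputs.

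| Planned output | SAP section | Set | Person appears? |
|---|---|---|---|
| Tables for each AE category | 6.4.2 | SAF-LTF | No |
| Listing of all AEs collected in 16996 | 6.4.2.1 | SAF-LTF | No |
| Summaries of 16996-emergent AEs, including new primary malignancies and fractures | 6.4.2.2 | SAF-LTF | No |
| Death table and listing | 6.4.2.3 | undefined label, read as SAF-LTF | No |
| Disposition, with reasons for withdrawal | 6.1.1 | ENR | Yes, in overall totals |
| Protocol deviations | 6.1.3 | ENR | Yes |
| Survival status listing | 6.2 | none named | Possibly |

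4. Possible gaps in this trace.
- SAP Section 6.4.2 also promises listings by AE category without naming a set, but the same paragraph takes SAF-LTF as its default.
- SAP Section 5.1 allows listings on ENR or SAF-LTF as applicable, but produces them by feeder trial arm, and this person is left out of those groupings.
- Neither statement gives the person's AE a place.

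5. Deaths. Death is a withdrawal reason in Protocol Section 4.4.1, so it could be counted among the ENR withdrawal reasons in SAP Section 6.1.1. SAP Section 5.3 assigns summaries of premature discontinuation to SAF-LTF, so that route is not certain. The survival status listing is a second possible route. Neither would show a leukemia or a fracture as such.

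6. Stated reason. SAP Section 4.1 justifies replacing the protocol set by the decision not to combine feeder data from patients who never enrolled in 16996. That reason does not cover people who did enroll. SAP Section 7.2 discloses how they are assigned, but not that their AEs leave the AE tables and listings.

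**The case against.** Several points on the other side stand, and they limit the claim.

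- **Conflict with the protocol.** A reader might infer that the SAP breaks a promise to include every enrollee in the safety evaluation. The documents support this only weakly. Protocol Section 3.2 defines feeder trials as selected company-sponsored radium-223 trials, so the protocol's Safety set (Section 8.2) is already limited to people dosed in selected trials. If eligible means selected, SAF-LTF adds no new restriction for enrollees. Protocol Section 3.3 describes people who meet inclusion criterion 1 and makes no explicit commitment about anyone enrolled in breach of it. Such people would be protocol deviations, which are reported on ENR.
- **Loss of all trace.** A reader might also infer that these deaths and serious events vanish. They do not necessarily. Deaths have the two possible routes shown above, and Protocol Section 7.5.1.4 still requires 24-hour reporting of malignancies, and of fractures that meet the SAE criteria. The Health Authority analyses are in a supplemental SAP that is not available here. SAP Section 5.5 organises them by applicable feeder study, so nothing shows that they would cover this group.
- **Size.** It is tempting to quote a large relative loss: with 4 cases of one type among about 800 enrolled, losing one moves 4/800 = 0.50% to 3/799 = 0.38%, a quarter of the cases. That assumes that a case falls in the excluded group. For the pooled malignancy category, the ALSYMPCA figure in Protocol Section 1.1 (7 of 600 in the radium-223 arm) would imply 800 × 7/600 = 9.3 cases, so one case is about 11%. If 1% of enrollees were non-eligible (an assumption) with equal risk, the chance of losing any of 4 cases is 1 − 0.99^4 = 3.9%. The answer depends wholly on inputs that the documents do not give.
- **Existence.** The SAP rule may be a precaution. Nothing says that anyone in this group received radium-223.

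None of this supplies an AE table or listing in which the event would appear.

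**Conclusion.** The point holds as a conditional statement about a written rule. Followed as written, the SAP leaves any malignancy or fracture collected in an exposed enrollee from a non-eligible feeder trial out of every planned AE table and AE listing. This rests on two readings: that the undefined label in the deaths section means SAF-LTF, and that listings with no named set follow the section's SAF-LTF default.

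The size is unknown. The number of such enrollees and their exposure are not given and may be zero. The documents do not support a claim that a safety signal has been or will be hidden, nor that the SAP plainly contradicts the protocol. What they support is an inexpensive correction that is worth making because the events of interest are rare and the data are already being collected.

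**What to change.** - Keep the by-arm SAF-LTF tables unchanged.
- Base the listing of all collected AEs (SAP Section 6.4.2.1) and the death listing (SAP Section 6.4.2.3) on ENR. Add one flag for feeder-trial eligibility and one for radium-223 or placebo exposure where known.
- For enrollees outside SAF-LTF, report N and the event counts in each primary AE category, separately from the arm columns.

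To apply the eligibility flag consistently, SAP Section 4.2 should say which trials count as eligible.

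The cost is SAP wording, two flag variables and a short extra display. AE data for these people would already be in the 16996 database, and Protocol Section 4.5 has sites record the previous study and subject numbers, so the feeder trial can be identified. The downside is a small, heterogeneous extra group. Its exposure data may be incomplete, because SAP Section 5.2.1 does not integrate data from non-eligible trials. If the group is empty, the display says so.

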5.1 General Principles

Long-term follow-up data may have been collected within the feeder study, within study 16996, or both. However, only follow-up data (e.g. adverse event data and anti-cancer medication/therapy data) that are collected during study 16996 will be included in the analyses described in this SAP. Limited information from feeder studies will be integrated with study 16996 (Section 5.2.1) to provide summaries of treatment exposure, overall follow-up duration and baseline characteristics at entry into feeder study. As noted in Section 7.2 below, this reduced analysis represents a deviation from the protocol-planned analysis.

Except if otherwise specified, participants will be included in the analyses according to the treatment they received in their feeder trial. Summaries will be presented by indication, feeder study and treatment arm within the feeder study. Listings will be produced by feeder trial arm containing participant data from study 16996, based on the ENR or SAF-LTF set, as applicable.

No formal statistical testing is planned for the overall analysis. The statistical evaluation will be performed by using the software package SAS release 9.4 or higher (SAS Institute Inc., Cary, NC, USA). Data will be analyzed using descriptive statistical methods.

Unless otherwise specified, the following descriptive statistics will be presented in data summaries:

- For continuous or ordinal data, the number of participants with data available (n), arithmetic mean, standard deviation (SD), minimum (min), quartile, median, maximum (max) will be presented.
- For categorical variables, the number of participants and percentage in each category will be presented.

The structure of analysis datasets and layout of analyses and data displays will follow Bayer AG standards, including Therapeutic Area Oncology Standards (TAS) and the Global Medical Standards (GMS), as applicable.

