#### 8.3.2 Statistical and analytical plans

*Section modified by Amendment 1 (Section 13.1).*

Studies of all clinical phases with different designs and different endpoints will be included in the evaluation. There will be separate analyses of the individual feeder trials, and pooled analysis of the final data across studies, as appropriate.

All statistical analyses will be descriptive in nature. In general, summary statistics (n, mean, standard deviation, median, minimum, maximum, and 95% confidence intervals for continuous variables, and number of subjects and percentage in each category for categorical variables) will be provided.

No formal statistical testing is planned for the overall analysis. Source data for summaries will be presented as subject data listings.

The details for analyses will be specified in the SAP.

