### **8.4 Determination of sample size**

Sample size calculation is not applicable for this follow-up study. All subjects from the feeder trials may participate in this study on a voluntary basis.

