- 16996-emergent new primary malignancies;
- 16996-emergent bone fractures;
- 16996-emergent serious bone fractures;
- 16996-emergent bone-associated events;
- 16996-emergent serious bone-associated events;
- 16996-emergent pregnancy AEs;
- 16996-emergent febrile neutropenia and hemorrhage without regard to cytotoxic chemotherapy status.

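### Primary incidences are planned as number and percent only, so a zero or one-case result for leukemia, MDS, aplastic anemia or primary bone cancer will not show what incidence remains compatible with the data

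*SAP*

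**What the plan says.** SAP 3.1 and Protocol 3.2 list the primary variables. All are incidences (with severity added for related adverse events), so all are summarised as categorical data.

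- **SAP 5.1**, general display rule: "For categorical variables, the number of participants and percentage in each category will be presented". The list for continuous data has no confidence interval either.
- **SAP 6.4.2**, each adverse event category: "a summary of the total number and percent of SAF-LTF participants with an AE of the applicable category", then a breakdown by preferred term, system organ class and grade for participants who had such an event.
- **SAP 6.4.2.2**: "Summaries of the total number and percent of SAF-LTF participants with an AE of the following categories of 16996-emergent AEs will be presented". One listed category is "16996-emergent new primary malignancies", a composite that SAP 6.4.2 defines to include leukemia, MDS, aplastic anemia, primary bone cancer and any other new primary malignancy.
- **Protocol 8.3.2**: "95% confidence intervals for continuous variables, and number of subjects and percentage in each category for categorical variables".
- **Protocol 8.4**: "Sample size calculation is not applicable for this follow-up study".

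Protocol 8.3.2.1 named incidence proportion, incidence rate and cumulative incidence as possible measures. The document history in SAP 7.1 records that version 2 removed the last two. The default rules in SAP 5.1 and 6.4.2 allow exceptions, but no later section uses one to add an interval.

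**The concern.** The study exists to characterise late events that may appear years after exposure (Protocol 1.2). For the rarest of them, a useful answer is the range of incidences the data still allow. A bare percentage does not give that range, and no sample size or precision statement elsewhere in the plan supplies it.

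Sparse results are realistic for these events. Protocol 1.1 reports no myelodysplastic syndrome and no bone sarcoma in radium-223 studies so far, one acute promyelocytic leukemia, and one aplastic anemia in each ALSYMPCA arm. SAP 5.1 then splits summaries by indication, feeder study and arm, so each denominator is smaller than the study total. A zero count with 0% can be read as absence of risk, although its meaning depends strongly on how many participants stand behind it.

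There is a second, smaller gap. The preferred-term breakdown covers participants with an applicable event, and no emergent category is reserved for leukemia, MDS, aplastic anemia or primary bone cancer separately. Nothing in the text ensures that a zero for one of them is printed at all.

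**Working it through.** The plan states no precision or power figure, so there is none to reproduce. The check asks what a zero or one-case result would mean.

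**Inputs.** N = 800 is the approximate enrolment expected in Protocol 3.1, with radium-223 and placebo together. Arm sizes are not given, so N = 400, 200, 100 and 50 are assumptions used to show the range. The 95% level comes from Protocol 8.3.2; two-sided is taken as the convention.

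**Formulas (exact Clopper-Pearson).**

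- 0 cases: lower limit 0; upper limit 1 − 0.025^(1/N).
- 1 case: lower limit 1 − 0.975^(1/N); upper limit is the 0.975 quantile of Beta(2, N − 1).

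Example: 0 of 800 gives 1 − 0.025^(1/800) = 1 − exp(−3.6889/800) = 0.0046, that is 0.46%, or about 1 in 217.

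| N | Source | 0 cases: upper limit | 1 case: percent (95% limits) |
|---|---|---|---|
| 800 | Protocol expectation, arms combined | 0.46% | 0.125% (0.003% to 0.69%) |
| 400 | assumed | 0.92% | 0.25% (0.006% to 1.39%) |
| 200 | assumed | 1.83% | 0.5% (0.013% to 2.75%) |
| 100 | assumed | 3.62% | 1% (0.025% to 5.45%) |
| 50 | assumed | 7.11% | 2% (0.051% to 10.65%) |

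The zero-case upper limit differs about 15-fold between N = 50 and N = 800 (7.11/0.46), while the planned cell shows the same count and percent.

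**Chance of seeing any case**, 1 − (1 − p)^N, for illustrative true incidences p:

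- p = 0.1%: 33% at N = 400 and 55% at N = 800. A zero at N = 800 would then occur 45% of the time.
- p = 0.5%: 98% at N = 800.

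**Where the sparse-data argument stops.** Protocol 1.1 gives ALSYMPCA counts for new primary malignancies: 7/600 = 1.17% (0.47% to 2.39%) on radium-223 and 5/301 = 1.66% (0.54% to 3.83%) on placebo. The composite is therefore not obviously a zero-count endpoint. The argument applies to the named rare components.

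**The case against.** Several points on the other side have force.

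- **No broken commitment.** A reader might infer that the SAP silently dropped intervals promised for the primary incidences. The documents do not support that. Protocol 8.3.2 already planned only counts and percentages for categorical variables, and SAP 5.1 matches it. The SAP does omit the protocol's intervals for continuous variables, but none of those is primary.
- **Unseen documents.** A reader might also infer that health authorities will receive no intervals. SAP 5.5 places those analyses in a separate supplemental SAP, and SAP 5.1 refers to sponsor display standards. Either may add intervals. The point holds for this SAP only.
- **Readers can compute the interval.** With the count and the denominator, they can. No data are lost. What is missing is a pre-specified method, level and presentation, and where no zero row is printed the reader must first infer the zero.
- **Not all primary variables are sparse.** Fractures, bone-associated events and related adverse events are also primary, and nothing in the documents shows that they are rare. This limits the argument to the marrow and bone malignancies.
- **A binomial limit can be over-read.** Death and dropout shorten follow-up, planned follow-up differs between indications (5 and 7 years), and SAP 5.1 counts only events collected in 16996. An upper limit is not a bound on long-term risk. This stands and determines how the interval must be labelled.

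That the study is descriptive and plans no formal testing is a weaker reply: an interval is estimation, and Protocol 8.3.2 itself lists intervals among its descriptive statistics.

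**Conclusion.** The point holds as an omission in reporting, not as an error or an undeclared deviation. For leukemia, MDS, aplastic anemia and primary bone cancer, the SAP as provided would present a zero or one-case result with no indication of the incidence still compatible with it. After no cases, that incidence reaches 0.46% at the expected 800 participants and 7.1% in an assumed arm of 50. The limit at 800 combines radium-223 and placebo; limits for radium-223 alone would be wider by an amount the documents do not allow one to compute.

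These figures treat each participant as one binomial observation over whatever follow-up occurred. They describe the observed incidence proportion and do not replace the time-based measures that version 2 removed. The small denominators are assumptions, and the supplemental SAP could close part of the gap.

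**What to change.** Amend SAP 5.1 and 6.4.2 as follows.

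1. Give the exact (Clopper-Pearson) two-sided 95% confidence interval with each primary incidence, by feeder study arm. In any summary pooled across feeder studies, give it separately for radium-223 and placebo, not for a column that mixes them.
2. Print separate rows for leukemia, MDS, aplastic anemia and primary bone cancer, including when the count is zero.
3. State that the interval applies to the incidence proportion observed over the actual follow-up, show it next to the follow-up duration summary of SAP 6.1.1, and do not present it as a bound on 5-year or 7-year risk.
4. List the interval in SAP 7.2 as an addition to the protocol-planned analysis.
5. Check that the supplemental SAP for Health Authority Reports follows the same convention.

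The cost is a few SAP sentences, one extra table column and four fixed rows; no new data are needed. The drawback is that results in small arms will look less reassuring.
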